7.9 Application of study medication

As mentioned before a venous access is installed at the forearm not used for experimental measurements.

There are two different treatment options every volunteer receives during the two experimental interventions.

- A) No medical or open label placebo (OLP) treatment during the intervention.
- B) Application of OLP 30 min after calibration for NRS 6.

7.10 Open label placebo application

Open-label placebo is given during Treatment B. A pain expert of the study stuff (the same person for one participant during the two interventions) applies placebo in treatment B. For an open-label placebo application the volunteer is orally informed that he will receive an intravenous placebo ("medical" not active substance) now. To strengthen positive expectations the study nurse assures the patient that placebos can have a strong effect on pain before application of the syringe content. The placebo is then injected intravenous while the investigator ensures that the volunteer watches the injection. The oral information text is standardized is exactly the same in every participant. (For the orginal text in german language cp. appendix)

7.11 Achievement of blinded medication application

A venous access is placed before every intervention session starts. An infusion of Ringer lactate with an infusion speed of 100ml/h (controlled via infusion pump) will be attached. The investigator performing the testing during the intervention leaves the test-room before possible placebo application. He is blinded if treatment A or B is applied. This, to ensure objective data collection.

The randomisation code is kept in a locked up folder in the office of the principle investigator [name] with restricted access only to the in intervention planning involved study personal, namely: [name] and [name]

Unblinding is done after the last last experimental intervention. The Randomization is than open to the study stuff taking part in the analysis of obtained data.

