7.2 General study design and justification of design

An assessor-blinded, randomized crossover study design will be applied. Each patient will undergo each of the two treatments (A-B) listed below. Furthermore, patients will be randomized to either receive placebo education or to not receive placebo education (e.g. B_1 = placebo education; B_2 = no placebo education). In other words, each patient will receive one of the two following treatment sets: either (A, B_1) or (A, B_2); the individual components of these sets will be randomized.

TREATMENT	General (visible)	Open drug application	
A→ No treatment	Infusion RL	No	
intervention	Infusion rate: 100ml/h		

B _{1,2} →Open-label	Infusion RL	OLP
Placebo alone	Infusion rate: 100ml/h	

Table 1: Overview study interventions

In each treatment the patient will receive a standard infusion containing only Ringer lactate (RL) infused at a rate of 100ml/h. The purpose of this infusion is simply to keep venous access.

To avoid any systematic bias the assignment of the study groups will be performed in a balanced randomized manner. To control for excitement and habituation effects we operate the interventions in a randomized order in every participant.

The participants are recruited by an advertisement on the University of Basel homepage and eligible volunteers will be included on a "first come, first served" basis.

Study participants are orally and written informed about study aims and interventions before the first assessment.

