7.3 General participant information

Every participant is informed that he will receive an open label placebo during one of the two interventions and no treatment in the other intervention. In addition, every participant receives the explanation that a placebo is an inactive substance therefore contains no active ingredient. A general explanation of the term "placebo effect" is also given to every volunteer.

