7.5 Experimental design

Acute pain will be induced through electrical stimulation in an established model first described by [name] et al.[16]. (For detailed experimental setup cp. Chapter 7.6-7.7)

Before the first intervention participants will be randomized to:

- 1) A placebo education group
- 2) A non-placebo education group

Participants in both groups will undergo the pain model two times. Every participant will receive treatment as follows in a sequential cross-over design (cp fig. 1).

[figure not shown]

Figure 1: Experimental design

During every experiment levels of saliva cortisol levels are collected at baseline, 30min, 60min and 100min after pain induction (cp. Fig. 4).

A washout period of two weeks well be instituted to prevent contamination (cp. Fig 1).

Randomization as well as preparation and application of the hidden and not hidden study medication will be executed by study stuff not involved in assessments during the intervention. During the individual experiment pain scores, hyperalgesia and allodynia will be assessed and documented by an investigator blinded to the treatment group.

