7.8 Procedures/ Recordings/ Interventions before and during electrical stimulation

Measurement of pain:

After adjusting for habituation as delineated above, pain, hyperalgesia, and allodynia will be assessed every ten minutes after time-point for possible OLP-application, using the NRS until the end of the individual session after 100 minutes (cp.Figure 4).

Measurement of hyperalgesia and allodynia:

Immediately after every pain rating the area of pinprick hyperalgesia is determined using a 256 mN von Frey filament and allodynia is determined using a dry cotton swab. Measurements are conducted from a more distant to a more central site along four orthogonal lines (distal, proximal, lateral, and medial) that will be drawn onto the skin with tick marks indicating each centimetre (cp. picture 1). Distal and proximal measurements will begin 12cm from the site of electronical stimulation; whereas the lateral and medial measurements were begin 6cm from this site. In both cases the used filament will be moved towards the site of stimulation in 0.5 cm increments until the subject reports either increased pain sensations from the von Frey filament (hyperalgesia) or an unpleasant "rougher" sensation from the cotton swab (allodynia). To create an area from these linear measurements, the assumption is made, that this field has the shape of an ellipse. The area is calculated using the formula $1/4\pi D \cdot d$.

Pain, hyperalgesia and allodynia measurement are exactly the same in both experimental interventions.

Picture 1: A: microdialys catheter inserted intra-cutaneous at the forearm; B: testing hyperalgesia with 256 mN von Frey filament; C: testing allodynia with a cotton swap.; adopted with permission from Mauermann et al., Anesthesiology, 2016. 124(2): p. 453-63.

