Appendix:

Text of the assessor direct before placebo application

The text will be recited and is exactly the same in every participant (German language):

"Ich werde ihnen nun ein Placebo in die Vene verabreichen. Wie sie bereits aus den Studieninformationen wissen, enthält ein Placebo keine medizinisch aktive Wirksubstanz. Wir wissen aus der aktuellen wissenschaftlichen Forschung, dass die Gabe eines Placebos einen starken positiven Effekt auf Schmerzen hat. Ich bin daher sehr zuversichtlich, dass dies auch bei ihnen zu einer deutlichen Reduktion der Schmerzen führen wird."

During this announcement the assessor is facing the participant and speaks with a calm, friendly voice. It is always the same person, who makes this speech.

[figure not shown]

[figure not shown]
The subsequent application is good visible for the participant and the saline is injected slow over at least 30 seconds via two ml syringe, clearly recognisable for the participant.

Slides of the Presentation for the "Placebo education group" with oral given information in text form:

[figure not shown]
Starting slide

Oral information: 83 patients with chronic low back pain were enrolled in this study. The first group received a treatment as usual (consisting of physical therapy and NSAID) and the second received an open label placebo in addition to the treatment concept in group one. The result was a statistical and clinical relevant better pain relief and disability improvement in the placebo group compared to the treatment as usual group.

Oral information: 80 patients with IBS diagnosed by Rome III criteria were randomized to either open label placebo or no treatment control. The primary was the global improvement score. Secondary outcomes were symptom severity score, percent of adequate pain relief, and improvement of quality of life. For all outcomes significant better results in the open placebo group were obtained.

Die Autonome Resonanz des Körpers auf ein Placebo

- Vorerfahrungen prägen die Reatkion unseres Körpers auf die Applikation einer Substanz.
- Diese Prozesse laufen nicht unbedingt im "Bewusstsein" sondern teilweise unterbewust ab.
- Die Eigenschaften eines Verums (z.B. Schmerzmedikament) können so zum Teil auf ein Placebo übertragen werden. (Benedetti et al. J Neurosci 2007; Colloca et al. Pain 2016)

Quelle: Dieter E. Zimmer: Das Placabo und sain Effakt. DIE ZEIT/Wissen, Nr.42, 8.Oktober 1998,

[figure not shown]

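### Nothing in the available text protects the assessor blind against disclosure by the participant, who knows his treatment and is then tested face to face

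*Combined protocol and SAP*

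**What the plan says.** Section 7.2 labels the trial: "An assessor-blinded, randomized crossover study design will be applied". Several measures support the label.

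- Section 7.11: the tester "leaves the test-room before possible placebo application. He is blinded if treatment A or B is applied".
- Section 7.5: randomisation, preparation and application "will be executed by study stuff not involved in assessments during the intervention".
- Section 7.11: "The randomisation code is kept in a locked up folder in the office of the principle investigator", with restricted access, and it is opened only after the last session.
- Section 7.4: the tester takes no part in the placebo education.
- Sections 7.2 and 7.11: the same Ringer lactate infusion, at the same rate, runs in both sessions.

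The participant is unblinded by design. Section 7.3 has every participant told that "he will receive an open label placebo during one of the two interventions and no treatment in the other intervention". In treatment B the placebo is announced to him (section 7.10), and the Appendix adds that "the saline is injected slow over at least 30 seconds via two ml syringe, clearly recognisable for the participant".

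After the time point for the possible injection, the blinded investigator assesses pain, hyperalgesia and allodynia every ten minutes to minute 100 (sections 7.5 and 7.8). For the skin mapping he moves the filament inward in 0.5 cm steps "until the subject reports either increased pain sensations from the von Frey filament (hyperalgesia"; allodynia is mapped the same way with a cotton swab.

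**The concern.** The stated measures control what the tester can see or look up. They do not control what the participant can tell him. The participant has to speak at every round, and he knows whether he was injected. Each participant has exactly one A and one B session, so whoever learns the treatment of one session knows the other.

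The tester elicits the NRS and maps the areas by hand, and section 7.11 gives objective data collection as the reason for blinding him. Since the participant cannot be blinded, this is the only blinding at measurement. If it fails unrecorded, the final report cannot support the assessor-blinded label.

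**Working it through.** The plan gives no figure on this point, so there is none to reproduce. The check is of the text, plus two small pieces of arithmetic.

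**1. What each safeguard closes**

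| Safeguard | Section | Route closed | Stops a remark by the participant? |
|---|---|---|---|
| Tester leaves the room | 7.11 | Seeing the injection | No |
| Separate staff randomise and apply | 7.5 | Handling the treatment | No |
| Code locked until the last session | 7.11 | Reading the allocation | No |
| Tester not part of education | 7.4 | Learning the education group | No |
| Same infusion in A and B | 7.2, 7.11 | A visible difference in set-up | No |

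**2. Where an instruction could stand.** Section 7.3 (general information), 7.6 (familiarisation), 7.10 (announcement) and 7.12 (requests to participants on medication, alcohol, exercise, caffeine, food and tooth brushing) contain none about keeping the treatment from the tester. No section plans a record of unblinding. No section fixes the length of the tester's absence, although B contains an announcement and an injection of at least 30 seconds and A contains neither. Section 7.12 also times two saliva samples from completion of the application, which does not occur in A.

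**3. How much of the data one remark exposes.** Section 11.2 gives 7 NRS measurements per session, which matches minutes 40 to 100 in ten-minute steps: (100 − 40)/10 + 1 = 7. Two sessions give 14. For a remark just before rating j (j = 1 to 7):

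- Session 1, same assessor in both sessions: (8 − j) + 7, so 14 down to 8 of 14 ratings.
- Session 1, a different assessor in session 2: 8 − j, so 7 down to 1.
- Session 2: 8 − j, so 7 down to 1. The session 1 ratings are already recorded.

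If the session 1 treatment is disclosed before session 2 ratings begin, all 7 session 2 ratings are exposed. The setting of the current to NRS 6 would be exposed too if the tester does it; section 7.7 does not say who does.

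**4. Whether random order cancels the effect.** Suppose an aware tester shifts session 2 results by δ in the hypothesised direction. In order A then B, B falls by δ and B − A changes by −δ. In order B then A, A rises by δ and B − A again changes by −δ. The sign is the same in both orders, so balancing the order does not remove it. The documents give no basis for a value of δ.

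**5. Sensitivity of the mapped areas.** Section 7.8 takes area = (π/4)·D·d. With radii a = D/2 and b = d/2, stopping one step (0.5 cm) nearer the site on all four lines gives a proportional loss of 1 − (a − 0.5)(b − 0.5)/(ab). The radii are assumptions; the documents give none.

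| a / b (cm) | ab | (a − 0.5)(b − 0.5) | Loss of area |
|---|---|---|---|
| 3 / 2 | 6 | 3.75 | 37.5% |
| 4 / 2.5 | 10 | 7 | 30% |
| 5 / 3 | 15 | 11.25 | 25% (47.1 to 35.3 cm²) |
| 6 / 4 | 24 | 19.25 | about 20% |
| 8 / 4 | 32 | 26.25 | about 18% |

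**The case against.** Four stronger readings are tempting, and the documents do not support them.

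- A reader might infer that the blind rests on nothing but leaving the room. The locked code, separate staff, exclusion from the education and identical infusion contradict this. They leave one route open, not all of them.
- A reader might infer that any single remark unblinds both sessions. That holds only for a remark in session 1, only from that moment on, and only if the same assessor tests twice. No section says so: the same person in section 7.10 is the one who applies the placebo.
- A reader might infer that participants are never told to stay silent. The participant information sheet and the session schedule figure are not in the reviewed text, so the statement covers the available text only.
- A reader might take the area losses as the expected bias. They assume the radii and a full step on every line, although movement stops when the participant reports a change, not when the tester decides. They also concern secondary outcomes.

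Further limits stand. The primary outcome is a number spoken by a participant who is unblinded by design, and his own expectation would remain under perfect assessor blinding. Knowing A from B reveals nothing about education group. Cortisol is an assay result. On absence, the tester leaves in both sessions and the ratings follow a common clock, so nothing shows that the lengths differ; the equality is simply unwritten.

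What the objection does not meet is the open route itself. No stated measure addresses disclosure by the participant, and no record would show whether it happened.

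**Conclusion.** The point holds in limited form. Within a session, absence from the room is the only stated barrier between the tester and the injection, and the available text neither asks for non-disclosure nor records unblinding. The exposure from one remark runs from 1 to 14 of a participant's 14 rating rounds; more than 7 requires a remark in session 1 and the same assessor in both sessions.

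The risk falls mainly on the mapped hyperalgesia and allodynia areas and on how the NRS is elicited. The 18% to 38% range shows how strongly the areas respond to one step at assumed radii. No size can be put on the primary comparison from the documents. The change is worth making because it is nearly free and protects the only blinding at measurement.

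A separate matter needs reconciling. The table of visits in the study schedule has the study nurse apply placebo with the investigator absent; section 7.10 has the investigator ensure that the volunteer watches; the Appendix has the assessor make the announcement facing him. Read literally, the Appendix would break the blind without any remark, and a silence instruction would not repair that.

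**What to change.** - **Section 7.3:** add a standard instruction not to say or hint to the tester whether an injection was given. Repeat it at the start of each session and before the tester returns.
- **Section 7.11:** set one absence time, the same in A and B, and require syringe and waste to be removed before re-entry.
- **CRF:** add one line to record any unblinding, with session and time, and report the entries.
- **Optional:** an assessor guess at the end of each session. Interpret it with caution: a correct guess may reflect an observed treatment effect, and the session 2 guess is not independent of session 1.
- **Separately:** reconcile the study schedule table, section 7.10 and the Appendix on who is present at the injection.

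The cost is a short instruction, one CRF line and a few minutes of waiting per session. No extra staff or visits are needed. The change does not remove the participant's own expectation bias, and the report should say so.

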7.12 Collection and processing of biomarkers

Saliva collection and processing

Oral fluids are collected to measure cortisol levels in response to induced pain. To control for diurnal variations of neuroendocrine parameters all experiments will be carried out between 4pm and 7pm.

Consistent with the procedures incorporated be Dickerson et al. [35] we decided to obtain the biological parameters in this study from oral fluids. Saliva levels of cortisol [36] are reliable and highly correlated with plasma levels. Therefore it is a less reactive, less invasive but reliable method to measure neuroendocrine immune activity.

To ensure a non-contaminated measurement participants are asked:

- Not to use non-prescription medications or alcohol within 24 hours before measurement
- To refrain from exercise and caffeine at least 2 hours to testing session
- Not to eat foods that may cause bleeding of the gums (e.g. potato chips) or brush their teeth for at least 2 hours prior to testing session.

Collection of saliva for cortisol determinations

A collection device (Salivette®) is placed into the mouth on the top of the tongue for 2.5min per sampling time point. Cortisol in saliva is in its unbound biologically active form and its concentration is independent of saliva flow rate [37].

Time points of measurements

Basic value:

After arrival of the participant for the intervention a 15 min rest must be hold before the first collection. The first collection during the first experimental intervention is to make the participant familiar with the procedure and will not be used for later analyses. A second collection will be performed directly after the test collection.

Further collections:

Saliva will be further collected as follows during the experimental intervention (cp. figure 4):

- 1. 30 min after constant electrical stimulation before application of study medication
- 2. 30 min after completed application of the study medication
- 3. 60 min after completed application of the study medication

After collection the oral fluids samples are immediately refrigerated before being transferred and will be stored at -80°C until further analysis, if analysis cannot be performed within 6 hours after collection.

[figure not shown]

Figure 4: Schedule for measurement of pain, hyperalgesia, allodynia, biomarker collection and application of study medication during an individual study intervention session.

8. Medical products and Medications used during the study

8.1 Medication used:

Carrier solution: Ringer Lactat Fresenius 1000ml Infusion solution. License number: 42692 (Swissmedic); license holders: Fresenius Kabi (Schweiz) AG, Oberdorf NW

NaCl 0.9%: NACL Bichsel Inj. Lös 0.9% 10ml ampulle; license number: 29800 (Swissmedic); license holder: [name] AG, Interlaken

All medication will exclusively be used as an unaltered medical batch.

8.2 Medical products used for the pain model:

Current stimulator: Digitimer S7; Digitimer, Hertfordshire, United Kingdom

Microdialysis catheter: self-manufactured at the laboratory of [name] et al. University Hopsital Hannover

8.3 Medical products used for the infusion application/ patient monitoring:

Controlled Infusion application: Injectomat Agilia, Producer: Fresenius Kabi; PZN: 4377569

Infusion application: Original B. Braun Perfusor® Syringe 50 ml PZN: 00570097; Original B. Braun Perfusor® Line IV Standard, Luer Lock PZN: 06100642;

Venous catheterization: B. Braun Vasofix® Safety 20G or 18G, CE-number: 0123 Producer of all products: B. Braun Melsungen AG

Storage conditions:

Study medications are stored with the medications for regular pain treatment in the chronic pain unit, according to the manufactures specification at room temperature and protected from light.

9. Study population

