- To investigate the effect of education prior to an open label placebo application.
- To investigate the effect of open label placebo application on biomarkers of stress (saliva cortisol)

Outcome(s):

[figure not shown]
Primary outcome:

Pain response measured by the Area under the Pain Curve (AUPC) using the numeric rating scale (NRS) from minute 30 to 100 after inducing definded pain in an experimental setting. Main comparison: The effect of open label placebo v.s. no treatment intervention.

Secondary outcomes:

 The pain response measured by the AUPC (NRS every 10 minutes during electrical stimulation) will be used for further comparison of the two different treatment interventions every participant recieves during the study.

	 Regularly taking medication potentially interfere with pain sensitation (analgesics, antihistamines and calcium and potassium channel blockers) Neuropathy Chronic pain Neuromuscular or psychiatric disease Known or suspected kidney or liver disease 		
Measurements and procedures:	Healthy male adults are recruted via an advertisment on the homepage of the University of Basel. After informed consent, but before any intervention, the participiants are randomized to a placebo educated and a non-educated group. The education group will receive an education about placebos and their effects prior to study intervention during the placebo will be applied. Every participiant will pass trough two interventions with electrical induced pain, defined at a NRS of six for 100 minutes each. Between the sessions a minimal two weeks washout period will be hold. During the two interventions participiants beceive the following treatments delineated above in a randomized manner.		
Study medication/ Study product:	Intravenous application of: open label placebo (2ml saline 0.9%).		
Control intervention	During one intervention (A) we do not apply any treatment at all during the intervention time. This to control for habitation effects during current application and create a comparison.		
Number of Participants with Rationale:	Based on our sample size calculation, we will require 22 participants. Recent estimates state that some 20-30% of patients are placebo-non-responders. Consequently, we will include 29 patients. However, with an estimated drop-out of 10% we plan to recruit 32 paitents. Patients dropping out will be replaced.		

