5.2 Secondary outcomes

- The pain response measured by the AUPC (NRS every 10 minutes during electrical stimulation) will be used for further comparison of the two different treatment interventions every participant recieves during the study. We compare the participants received a education about placebo to the non prior educated participants.
- 2. Hyperalgesia and allodynia will be measured analogously to the NRS as above.
- 3. Saliva concentration of cortisol, measured at baseline, 30, 60 and 100 minutes after pain induction.

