11.2 Determination of sample size

Sample size has been determined by a Wilcoxon signed-rank test for the AUPC for Treatments A and B. The AUPC is the product of the NRS x Time. 7 measurements of NRS will be made in total, one every ten minutes. We expect the area under the curve to be 50 NRSxminutes based on a general difference of 1 NRS point and some time for the effect to fully develop. We expect the standard deviations in both groups to be 1 NRS or 60 NRS*min. Using a t-test with a 20% mark-up for non-parametric data we have arrived at a required number of patients of 22. However since 20-30% of participants can be expected to be non-responders to placebo [38] and expecting 10% drop out we have arrived at a total number of patients to be recruited of 32.

11.3 Statistical criteria of termination of the trail:

Upon completion. With such a small sample size, no interim analysis will be conducted.

11.4 Planned Analyses, Datasets, and Analysis Populations:

For the first hypothesis (AUPC for $B_{1/2}$ vs. A) we will conduct a Wilcoxon signed-rank test. Additionally, we conduct a mixed effects model using the AUPC as the dependent outcome and the treatment, the session order (e.g. Treatment B before Treatment A) time during electrical stimulation (in minutes), and finally the individual. This will allow for a more differentiated analysis accounting for temporal and sessional habituation in explaining the treatment effect.

For the effect of education, we will compare the AUPC of: Treatment B_1 vs Treatment B_2 , again by a Wilcoxon signed-rank test.

The outcomes hyperalgesia and allodynia, as well as biomarkers will be examined analogously to the respective comparisons with the AUPC.

11.8 Interim analysis:

Given the small sample size and limited time, no interim analysis will be conducted.

11.9 Safety analysis:

None. However, patients will be under the continuous surveillance of anesthesiology staff.

11.10 Deviation(s) from the original statistical plan:

The statistical plan will be published prior to commencement on clinicaltrials.gov. Any deviations from the statistical plan will be reported and justified in the final report.

11.11 Handling of missing data and drop outs:

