13.6 Confidentiality, Data Protection

Participant's confidentiality will be maintained at all times. The investigator affirms and upholds the principle of the participant's right to privacy and those they shall comply with applicable privacy laws.

Individual subject medical information obtained as a result of this study is considered confidential and disclosure to third parties is prohibited. Subject confidentiality will be further ensured by utilising subject identification code numbers to correspond to treatment data in the computer files. Personnel from the sponsor, the Pain Unit USB and members of IEC are obliged to respect medical secrecy and to refrain from divulging the participant's identity or any other personal information they might fortuitously be aware of.

Direct access to source documents will be permitted for purposes of monitoring, audits and inspections. All study personnel involved in this trial ([name], [name], [name], [name], [name], [name], [name], [name] and [name]) will have access to protocol, dataset during and after the study (publication, dissemination).

Demographic data and personal data will be kept in the electronic database. Subjects will receive a study number upon inclusion, and in the data base only the study number will appear. Only the principal investigators will have the key. Data generation, transmission, storage and analysis of health related personal data and the storage of biological samples within this project will follow strictly the current Swiss legal requirements for data protection and will be performed according to the Ordinance HRO Art. 5. Health related personal data captured during this project and biological samples from participants are strictly confidential and disclosure to third parties is prohibited; coding will safeguard participants' confidentiality. Project data will be handled with uttermost discretion and only be accessible to authorised personnel.

13.7 Storage of biological material and related health data:

NaCl 0.9% and Ringer's Lactate will be stored according to the manufacture specification at room temperature and protected from light. The infusion is prepared max. 1 hour before application. Saliva samples will be processed into different aliquots and kept frozen at -80°C until analysis, if analysis within 6 hours after probe drawing is not possible.

14. Publication and Dissemination Policy

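### Saliva is frozen only when it cannot be assayed within 6 hours, and nothing keeps a participant's two sessions in one run, so avoidable between-run error can enter the paired cortisol comparison

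*Combined protocol and SAP*

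**What the plan says.** Section 7.12 sets the handling rule: after collection the samples are refrigerated, transferred, and "will be stored at -80°C until further analysis, if analysis cannot be performed within 6 hours after collection". Section 13.7 has the same condition: aliquots are "kept frozen at -80°C until analysis, if analysis within 6 hours after probe drawing is not possible". Both sections treat freezing as what happens when analysis inside 6 hours is not possible.

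The synopsis (measurements and procedures) fixes the gap between a participant's sessions: "Between the sessions a minimal two weeks washout period will be hold". Section 7.12 adds that "all experiments will be carried out between 4pm and 7pm".

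Cortisol is the third secondary outcome in section 5.2: "Saliva concentration of cortisol, measured at baseline, 30, 60 and 100 minutes after pain induction". For its analysis, section 11.4 states: "The outcomes hyperalgesia and allodynia, as well as biomarkers will be examined analogously to the respective comparisons with the AUPC". For the AUPC comparison of B with A, that section says "we will conduct a Wilcoxon signed-rank test", so cortisol B versus A is also a paired, within-participant contrast. The cortisol comparison of B1 with B2 is between participants, because each participant belongs to one education group only.

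Under section 11.11 the cortisol samples are destroyed once analysed. The documents name no assay or laboratory and give no assay precision. They do not ask for samples to be batched by participant, for run or sample state to be recorded, or for run to enter the analysis.

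**The concern.** A paired comparison gains its precision from cancelling whatever the two sessions of one person have in common. A run's calibration error cancels only if both sessions are in that run. The rule allows, and for any session assayed fresh forces, the two sessions into separate runs. One session may also be assayed fresh and the other after freezing and thawing.

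At stake is the precision of the cortisol result. Section 7.12 works to limit other sources of cortisol variation through time of day, caffeine, exercise, food and tooth-brushing, but leaves this one open. It cannot be put right afterwards, since destroyed samples cannot be re-assayed together. The handling rule therefore has to be settled before the first sample is taken.

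**Working it through.** The plan has no cortisol figure to reproduce: no assay CV, SD, effect size or power. The check is a reading of the rule, followed by an illustration on stated assumptions.

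**When are the two sessions in different runs?**
- Both sessions assayed fresh: each within 6 hours of its own collection, at least two weeks apart. Different runs, necessarily.
- One fresh, one frozen: different runs, necessarily, and different states.
- Both frozen: same state. They may or may not share a run, because the text is silent on batching.

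**How much variance would a split add?** Work on the log scale and take the between-run log-SD as approximately the between-run CV. Let SD_d be the SD of a participant's A-B log difference when both sessions share a run.
- Same run: the run error is common and cancels, so the variance is SD_d².
- Different runs: two independent run errors remain, so the variance is SD_d² + 2·CV².
- Relative increase = 2·CV² / SD_d².

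Assumed inputs: CV 5%, 10%, 15%; SD_d 0.3 and 0.5; raw levels compared; every participant split across runs. The added term 2·CV² is 0.005, 0.020 and 0.045. SD_d² is 0.09 or 0.25. The equivalent number is 29 / (1 + increase), where 29 is the number of participants the synopsis plans to include before its drop-out allowance.

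| CV | SD_d 0.3: increase | equivalent n of 29 | SD_d 0.5: increase | equivalent n of 29 |
|---|---|---|---|---|
| 5% | 0.005/0.09 = 5.6% | 27.5 | 0.005/0.25 = 2.0% | 28.4 |
| 10% | 0.020/0.09 = 22.2% | 23.7 | 0.020/0.25 = 8.0% | 26.9 |
| 15% | 0.045/0.09 = 50.0% | 19.3 | 0.045/0.25 = 18.0% | 24.6 |

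If only a fraction f of participants is split, the average increase is f times these values.

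**In terms of power.** Take a paired t-test (two-sided 5%, standing in for the signed-rank test) that would have 80% power without run error. That 80% is a reference point, not a figure from the plan. With every participant split:
- SD_d 0.3: 78%, 72% and 63% at CV 5%, 10% and 15%.
- SD_d 0.45: 79%, 76% and 72%.

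These hold to within 0.1 percentage point for n of 22, 29 or 32.

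**What would reduce it?** If the summary is a log change from the same session's baseline, and baseline and later samples are in one run, the run error appears in both and cancels within the session. The increase then falls towards zero for a purely proportional run error. The plan does not define the cortisol summary, so this cannot be counted on. It would also fail if fresh and frozen samples were mixed within a session.

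**Fresh-versus-frozen shift.** Any such shift would come on top, in participants whose two sessions differ in state. The documents give nothing from which to size it.

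**The case against.** The strongest reply is that the 6-hour rule is only a maximum holding time for unfrozen samples. With sessions between 4pm and 7pm, the limit falls between about 10pm and 1am, so most samples will probably be frozen. A single batch at the end of the study would comply fully with the text. This stands in part. It makes regular mixing of fresh and frozen samples unlikely, and a reader should not infer that A and B samples always go into different runs: that is certain only when at least one session is assayed fresh. But the text does not say that all samples are frozen, and freezing alone does not put two sessions in one run.

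Three stronger readings are tempting and are not supported:
- *The result is biased towards one treatment.* Section 7.2 randomises treatment order, so run and state differences do not favour A or B on average. They add noise and chance imbalance.
- *Early samples of a session will be fresh and later ones frozen.* The clock starts at each sample's own collection. If a session's tubes travel together, the earliest expire first. The documents do not describe tubes being sent separately.
- *The loss is large.* The 50% figure needs the highest assumed CV, the smaller SD, raw levels and every participant split. At SD 0.5 and CV 5-10% the increase is 2-8%.

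It is also fair to say that cortisol is a secondary outcome with no power claim. The locked code in section 7.11 already gives substantial protection against an unblinded assay before the last session. These points limit the importance of the concern but do not remove it.

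**Conclusion.** The concern holds in a limited form. The written rule permits a participant's two sessions to be assayed in different runs, and requires it whenever a session is assayed fresh. Between-run error can therefore add variance to the paired cortisol difference. Treatment order is randomised, so there is no systematic bias, and the primary AUPC result is untouched.

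The size cannot be derived from the documents. Under the assumptions above it is about 2% to 50% more variance (2% to 22% at CV 5-10%). It is less if only some participants are split, or if the summary is a proportional change from a same-session baseline assayed in the same run. This is a cheap improvement to a secondary outcome. It is worth making because the loss is avoidable and cannot be recovered once samples are destroyed.

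**What to change.** In sections 7.12 and 13.7, delete the option of fresh analysis within 6 hours and state: *All saliva samples are frozen at -80°C. All samples of one participant, from both sessions, are thawed together and assayed in the same run by a laboratory without the treatment code. Each run includes participants from both education groups.*

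The last sentence is needed because keeping a participant's samples together does nothing for B1 versus B2, which could otherwise be confounded with run. With four analysed samples per session, two sessions and 32 participants there are 4 × 2 × 32 = 256 samples, so more than one run may be needed. Recording the run and reporting the between-run CV would let readers judge what remains.

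The cost is small. Cortisol results come only after each participant's second session, with a few weeks of freezer storage. Storage at -80°C is already planned, no interim analysis depends on early results, and no extra samples, visits or participant procedures are required.
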